5.5 Data Collection and Follow-up for Withdrawn Subjects

[figure not shown]
- All subjects who discontinue the trial prematurely will be followed.
- Every effort will be made to maintain contact with patients discontinuing treatment during the course of the trial.
- Reasons for withdrawal will be investigated and documented.
- All efforts should be made to document the outcome following the withdrawal.
- Patients who withdrew from the study will not be replaced.

6. STUDY TREATMENT

6.1 Study Drug

Azilect® tablets contain rasagiline (as the mesylate), a propargylamine-based drug indicated for the treatment of idiopathic Parkinson's disease. It is designated chemically as: 1H-Inden-1-amine, 2, 3-dihydro-N-2-propynyl-, (1R)-, methanesulfonate. The empirical formula of rasagiline mesylate is (C₁₂H₁₃N) CH₄SO₃ and its molecular weight is 267.34.

Its structural formula is:

Rasagiline mesylate is a white to off-white powder, freely soluble in water or ethanol and sparingly soluble in isopropanol. Each Azilect tablet for oral administration contains rasagiline mesylate equivalent to 0.5 mg or 1 mg of rasagiline base.

Each Azilect tablet also contains the following inactive ingredients mannitol, starch, pregelatinized starch, colloidal silicon dioxide, stearic acid and talc. The matching placebo will look exactly like the study medication to maintain the double blind design of the study.

6.2 Treatment Regimen

Subjects will be randomized to a 1:1 ratio to receive Rasagiline or the matching placebo 24-week double blind treatment.

Subjects will take one 0.5 mg rasagiline tablet or the matching placebo once a day on Baseline (Day 1) through Week 4. The dose will be titrated up to one 1 mg tablet or the matching placebo once a day starting **on Week 5** until the Week 28 (end of treatment visit).

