STUDY DESIGN	This is a Phase II, randomized, double blind, placebo controlled, parallel group, proof-of-concept three-site study, to evaluate the effect of rasagiline in the regional brain metabolism on FDG PET. The study consists of two phases: a 24-week double blind placebo controlled treatment period and a 4-week follow-up period. Patients will be randomized to a 1:1 ratio at Baseline to receive either rasagiline or matching placebo.

	
The study drug will be given as 0.5 mg dose once daily for the first 4 weeks; it will be increased to 1 mg daily for the next 20 weeks. A total of 50 subjects will be enrolled: 25 will receive rasagiline and 25 will receive matching placebo for the 24-week treatment period.

STUDY ENDPOINTS	
Primary Endpoint
 
The primary study endpoint is the change from Baseline to Week 24 in regional glucose metabolism as measured by standard uptake units regional (SUVr) obtained through the FDG-PET.
 
Secondary Endpoints
 
 • Change from Baseline to Week 24 in ¹⁸F-AV-1451 Tau PET imaging SUVr • Change from Baseline to Week 24 on the scores of MMSE, ADAS-Cog 11 and CGIC • Change from Baseline to Week 24 on the scores of NPI and ADCS-ADL • Change from Baseline to Week 24 on the scores of Digit Span test, COWAT and QoL-AD/Study Partner • Correlation between changes in clinical measures (rasagiline vs. placebo change from baseline) and SUVr for FDG PET and SUVr for ¹⁸F-AV-1451 Tau PET • Correlation between SUVr for FDG PET and SUVr for ¹⁸F-AV-1451 Tau PET • Safety and tolerability as measured by incidence of adverse events/serious adverse events (AEs/SAEs), clinical laboratory test data, vital signs, 12-lead EKG data • Proportion of subjects with adverse events, serious adverse events and adverse events leading to discontinuation over the 24-week double blind treatment period • Proportion of subjects with laboratory abnormalities • Proportion of subjects with EKG abnormalities
SAMPLE SIZE	
Target enrollment is 50 subjects and will be recruited from three sites of the Cleveland Clinic Lou Ruvo Center for Brain Health – Las Vegas, Cleveland Main Campus and Lakewood sites

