DIETARY ADJUSTMENT	
High tyramine-containing foods will be avoided:
 
 • Sausages, salami, pickled herring • Fava beans • Tap beers, non-pasteurized beers • Sauerkraut, yeast extract, soybean products including soy sauce • Aged cheeses
DRUG DOSAGE AND FORMULATION	
Subjects will take one 0.5 mg dosage Rasagiline tablet or the matching placebo once a day orally from Baseline visit to Week 4 visit. The dose will be titrated to one 1 mg dosage tablet or the matching placebo once a day starting on Week 5 through Week 24.

DURATION OF PARTICIPATION	
This is a 34-week study comprised of 7 in-clinic visits

PLACEBO	
A matching oral placebo will be used

ROUTE OF ADMINISTRATION	
Oral

PROCEDURES	
Physical and neurological exam, MRI, [18F]-FDG PET, ¹⁸F-AV-1451 Tau PET, ECG, vitals, clinical laboratory tests, MMSE, ADAS-Cog 11, CGIC, NPI, ADCS-ADL, Digit Span, COWAT, QoL-AD/Study Partner

STATISTICAL CONSIDERATION	
Intent-to-Treat (ITT) - The primary FDG analysis will include all patients who received both a screening and end of study scan of acceptable quality.
 
Modified Intent-to-Treat (mITT) – All randomized subjects who have been dispensed study medication and have one post-baseline visit during the blinded phase of the study.
 
Per-protocol (PP) population – All ITT subjects who complete the study (Week 24) and have ingested between 80% to 120% of the prescribed study medication as measured by pill count.
 
Observed case – An observed case analysis of all patients completing the study will be conducted.
 
Last Observation Carried Forward (LOCF) – Clinical data imputation will use the LOCF approach for missing patients.
 
Responder analysis – Responders will be defined as those that have a significant improvement on brain metabolism on FDG for the whole brain or for any of the pre-specified regions.
 
A secondary analysis will compare the changes in FDG at 24 weeks compared to the projected expected metabolism based on the Baseline FDG findings.

ADVERSE EVENTS	
SAFETY
 
Orthostatic vital signs, ECG, hematology, chemistry, TSH, B12 and urinalysis (UA) collected at Screening and at end of study

	
TOLERABILITY
 
Side effects data will be collected and converted to systems data using a data dictionary.
 
DSMB No Independent DSMB is required.

--	--

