4. STUDY DESIGN

This is a 24 week, Phase II, randomized, double blind, placebo controlled, parallel group, proof-of-concept three-site study, to evaluate the effect of rasagiline in the regional brain metabolism on FDG PET in patients with mild to moderate Alzheimer's disease.

The study consists of two phases: a 24-week double blind placebo controlled treatment period with a 4-week follow-up period. Patients will be randomized to a 1:1 ratio at Baseline to receive rasagiline or matching placebo treatment.

The study drug will be given as 0.5 mg dose once daily for the first 4 weeks then increased to 1 mg dose daily tablet for the next 20 weeks. A total of 50 subjects will be enrolled and will be randomized to a 1:1 ratio. Twenty-five participants will receive rasagiline and the other 25 will receive matching placebo for the 24-week treatment period.

Figure 5. **Research Schematic**

Visit 1 – Screening visit (within a 60-day period); MRI, FDG PET and ¹⁸F-AV-1451 Tau imaging

Visit 2 – Baseline (Week 1)

Visit 3 Week 4; increase dose from 0.5 mg QD to 1 mg QD

Visit 4 Week 8

Visit 5 –Week 24; blood draws, FDG PET & ¹⁸F-AV-1451 Tau imaging, end of treatment

Visit 6 – Follow-up Visit/ Week 28; end of study/early discontinuation

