6.3 Administration of Treatment

Study medication should be administered once daily, with or without food. Subjects will swallow all orally administered study medication as a whole and will not chew the medication before swallowing.

Patients will be given 1 month supply of 0.5 mg rasagiline or matching placebo tablets to take home on the day of randomization (Visit 2) with detailed instruction of taking one capsule once a day for 4 weeks. Patient is to return to clinic for Visit 3 (Week 4), when the dose will be increased to 1 tablet of 1 mg rasagiline or matching placebo once a day. Patients are to continue taking 1 tablet of 1 mg rasagiline or matching placebo once a day for the next 20 weeks of treatment.

Table 1 Group and Treatment Phases

Groups	Treatment Phases	
	Baseline to Week 4	Week 5 to Week 24
Active	1 x 0.5 mg rasagiline QD	1 x 1 mg rasagiline QD
Placebo	1 x matching placebo QD	1 x matching placebo QD

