6.7.3 Packaging of Study Drug

Study active medication and placebo will be packaged in 1-month supply bottles. There will be a total of 40 capsules in a bottle of either the rasagiline drug or the placebo. Each participant will return study medication bottles (including any unused study medication) at each visit for drug accountability purposes.

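### Protocol 6.2 runs 1 mg dosing to Week 28 and calls that the end of treatment; everywhere else treatment ends at Week 24

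*Protocol*

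**What the plan says.** Section 6.2 of the protocol gives two different lengths of treatment. Its first sentence randomizes participants to rasagiline or "the matching placebo 24-week double blind treatment". Its last sentence starts the 1 mg dose in Week 5 and continues it "until the Week 28 (end of treatment visit").

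The other statements on duration agree with the first sentence of 6.2:

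- Protocol synopsis, Study Design: "a 24-week double blind placebo controlled treatment period and a 4-week follow-up period".
- Protocol synopsis, Drug Dosage and Formulation: the 1 mg dose is taken "once a day starting on Week 5 through Week 24".
- Protocol section 4: "a 24-week double blind placebo controlled treatment period with a 4-week follow-up period", with 4 weeks at 0.5 mg and then 20 weeks at 1 mg.
- Protocol section 6.3: 1 mg is taken "once a day for the next 20 weeks of treatment", and Table 1 heads the 1 mg phase "Week 5 to Week 24".
- Protocol section 7.5: the Week 24 visit closes the treatment phase and is followed by four weeks of post-treatment safety follow-up.
- Protocol section 7.6: the Week 28 visit comes after the treatment phase.
- Protocol Table 2 and Appendix B: Visit 5 (Week 24) is labelled EOT and Visit 6 (Week 28) is labelled EOS.
- SAP section 2: 4 weeks at 0.5 mg, then 20 weeks at 1 mg, then a 4-week follow-up.

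**The concern.** Section 6.2 is where a pharmacist or coordinator would look for the stop date, and the date there is wrong. It also attaches the end-of-treatment label to the follow-up visit.

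If a site acted on that sentence alone, participants would take an MAO-B inhibitor or placebo for four more weeks, and the off-drug safety period would be lost. No ECG or laboratory test is scheduled after Week 24 (sections 9.5 and 9.7). Vital signs and adverse events are recorded at Week 28 under Table 2.

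Two smaller items also depend on the stop date. Compliance is judged against the prescribed dose, so a different stop date changes the denominator of the pill count. The Week 24 tau PET window is set relative to the last dose, so it would move as well.

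**Working it through.** **Inputs.** Dosing is one tablet daily: 0.5 mg for Weeks 1 to 4, then 1 mg from Week 5 (sections 4, 6.2 and 6.3). The stop date is Week 24 (all the sections listed above) or Week 28 (last sentence of 6.2). The final follow-up visit is at Week 28 (section 7.6).

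**Reproducing the plan's own figure.** Week 5 through Week 24 inclusive is 24 − 5 + 1 = 20 weeks at 1 mg, and 4 + 20 = 24 weeks in total. This matches the synopsis, section 4, section 6.3 and SAP section 2.

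**Section 6.2 taken literally.** Week 5 through Week 28 inclusive is 28 − 5 + 1 = 24 weeks at 1 mg, and 4 + 24 = 28 weeks in total. This contradicts the 24 weeks in the first sentence of 6.2.

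**Size of the difference, if the sentence were followed:**

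| Quantity | Stop at Week 24 | Stop at Week 28 | Difference |
|---|---|---|---|
| Doses (weeks × 7) | 24 × 7 = 168 | 28 × 7 = 196 | 28 (28/168 = 16.7%) |
| Cumulative active dose | 28 × 0.5 + 140 × 1 = 154 mg | 28 × 0.5 + 168 × 1 = 182 mg | 28 mg (28/154 = 18.2%) |
| Off-drug follow-up | 28 − 24 = 4 weeks | 28 − 28 = 0 weeks | −4 weeks |

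**Would the supply stop it?** From the Week 8 dispensing, 16 × 7 = 112 doses reach Week 24 and 20 × 7 = 140 reach Week 28. Section 6.7.4 gives a 4-month supply at Week 8 but no tablet count. Two readings are possible, and both are assumptions:

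- Four calendar months of daily doses is about 112 to 122 tablets, which would run out before Week 28.
- Four of the 40-count one-month bottles in section 6.7.3 is 4 × 40 = 160, which covers either stop date.

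The amount supplied therefore cannot be relied on as the safeguard. The safeguard is the return of drug ("Each participant will return study medication bottles (including any unused study medication) at each visit", section 6.7.3), together with the accountability check at Week 24 and the absence of any dispensing at that visit (section 7.5).

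**Would the pill count flag it?** The accepted range is 80% to 120% (section 6.4). Taking 196 doses against 168 prescribed is 196/168 = 116.7%, which is inside the range. In the other direction, full adherence to 24 weeks scored against 28 weeks is 168/196 = 85.7%, also inside. The 80% limit itself would move from 0.8 × 168 = 134.4 to 0.8 × 196 = 156.8 doses. Someone taking 135 to 156 doses would be compliant on the first denominator and non-compliant on the second.

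**Tau PET window.** Section 7.5 allows the scan from 14 days before to 7 days after the last dose. Counting Week 24 as day 168, a last dose then gives days 154 to 175. A last dose at Week 28 (day 196) gives days 182 to 203, which excludes the Week 24 visit.

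**After correction.** With Week 24 in 6.2, the sequence is 4 + 20 = 24 weeks on drug and 4 weeks off, in agreement with every other dosing statement.

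**The case against.** The strongest reply is that the documents already settle the matter. Section 6.2 opens with 24 weeks, the dosing table in the next section stops at Week 24, and the visit instructions that staff work from close the treatment phase at Week 24. A site would have to prefer one clause over all of these. On that view the extra doses and the lost follow-up are hypothetical, and the missing ECG and laboratory tests matter only within that hypothetical, since none is planned at Week 28 anyway. This stands, and it is why the point is minor and the figures above are upper limits rather than expected effects.

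One schedule entry could be cited in support of Week 28: Table 2 and Appendix B mark drug accountability at Visit 6. That does not rescue the sentence. Visit 6 also serves as the early-discontinuation visit, and a count of returned drug is not an instruction to dose.

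It can also be said that a site notice is unnecessary because section 7.5 already tells sites when treatment ends. That is arguable. The correction to 6.2 is the essential part, and the notice is a cheap precaution.

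**Conclusion.** The concern holds. The stop date in section 6.2 is wrong as written: it contradicts the opening of its own section, the rest of the protocol and SAP section 2, and no other dosing statement supports treatment to Week 28. It is most likely a slip of one week number.

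Severity is minor. The increases of 28 doses and 28 mg and the loss of four off-drug weeks apply only if a site follows that sentence over all the others, with every daily dose taken. The Week 24 primary FDG endpoint, the sample size and the 24-week clinical models do not change. Confidence is high, because the conclusion rests on plain text and week arithmetic. The only assumption concerns the number of tablets dispensed at Week 8, and the conclusion does not depend on it.

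**What to change.** In the last sentence of Protocol section 6.2, replace Week 28 with Week 24 and keep the end-of-treatment label. Send sites a short note that the last dose is at Week 24 and that Week 28 is an off-drug follow-up visit.

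The cost is one corrected number and a brief notice. Design, sample size, visit schedule and data collection stay as they are.

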6.3 Administration of Treatment

Study medication should be administered once daily, with or without food. Subjects will swallow all orally administered study medication as a whole and will not chew the medication before swallowing.

Patients will be given 1 month supply of 0.5 mg rasagiline or matching placebo tablets to take home on the day of randomization (Visit 2) with detailed instruction of taking one capsule once a day for 4 weeks. Patient is to return to clinic for Visit 3 (Week 4), when the dose will be increased to 1 tablet of 1 mg rasagiline or matching placebo once a day. Patients are to continue taking 1 tablet of 1 mg rasagiline or matching placebo once a day for the next 20 weeks of treatment.

Table 1 Group and Treatment Phases

Groups	Treatment Phases	
	Baseline to Week 4	Week 5 to Week 24
Active	1 x 0.5 mg rasagiline QD	1 x 1 mg rasagiline QD
Placebo	1 x matching placebo QD	1 x matching placebo QD

6.4 Subject Compliance Monitoring

Adherence to the study protocol will be judged by pill counts. Non-adherence of less than 80% of the anticipated dose will result in study discontinuation. Accepted drug compliance is compliance rate of 80% to 120%.

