5.4 Subject Withdrawal

Patients and caregivers are informed that they have the right to withdraw from the study at any time without prejudice or loss of benefit to which they are otherwise entitled.

The investigator or sponsor may withdraw a patient from the study in the event of an inter-current illness, adverse event, non-compliance, protocol violation and other reasons concerning the health or wellbeing of the patient.

Following are specific circumstances justifying withdrawal:

- Development of an inter-current medical condition or need for concomitant treatment that precludes further participation in the trial
- Unacceptable toxicity or any adverse event that precludes further participation in the trial
- The investigator removes the patient from the trial in the best interests of the patient
- Non-adherence to study regimen as determined by pill count
- Patient withdraws consent to continued participation in the trial

Patients who withdraw prior to study completion will be asked to return to the clinic to complete visit 6 (end of study) assessments.

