9.2 Concomitant Medications

Concomitant medications will be recorded at each visit based on the study partner interview and any other available information. After randomization, initiation of any excluded medication, or change in permitted agents will be discouraged. However, follow-up of all participants, regardless of compliance with medication restrictions, will be continued in order to maximize the data available for the intent to treat analysis.

Initiation during the study of medications which are excluded because of confounding effects on cognitive outcomes (such as sedating or anticholinergic medications) is discouraged, but will not require termination of study drug or exclusion from the ITT analysis. Cessation or change of anti-dementia therapies during the study is also discouraged, but will also not prevent continued participation in the protocol or inclusion in the intent to treat analysis.

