There are two FDG-PET scans to be conducted per participant in this study. The scans will be done at the Screening visit for study eligibility, and at Week 24 visit for end of treatment scan and comparison.

The scanning protocol and equipment qualification requirements for this study will be consistent with those implemented in ADNI 2 (30). FDG-PET imaging data will be obtained at two sites: the Cleveland Clinic facilities in Cleveland, Ohio and Las Vegas, Nevada. Each of these sites uses a Siemens Biograph PET/CT LSO 16 slice camera. As part of site qualification, site practices will be reviewed, along with recent equipment calibration logs. If the site has a 3D-Hoffman phantom

scan collected within the past 12 months available, the scan will be provided for examination. If a de-identified patient brain scan can be made available, it will be provided for examination. The requirements for subject management in preparation for the scan, during FDG uptake, and during image acquisition will be reviewed with staff to ensure that these can be met. Since the Cleveland Clinic participates in ADNI as well as numerous other clinical trials, it is anticipated that requirements will be met.

The scanner will have an up-to-date calibration and normalization on the date of each imaging session. A daily QC check will be done at the beginning of the day the scanning will be completed. The scan will be visually inspected for abnormalities. If there is a possibility that the abnormality could impact the PET scan quality, the visit will be rescheduled.

Daily CT quality assurance will be performed as recommended by the specific vendor, and should typically include a "checkup/calibration" procedure and a water phantom scan. The checkup/calibration procedure guarantees optimum image quality by warming up the x-ray tube and should be performed at startup and within 1 hour prior to any scan. The water phantom provides quality measurements of 3 parameters. The parameters are the CRT value of water calculated in Hounsfield units (HU), the pixel noise of images calculated as a standard deviation, and the tube voltages measured directly on the x-ray tubes. These three measurements should be determined for all available kVp values.

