11.2 Statistical Methods

Intent-to-Treat (ITT) - The primary FDG analysis will include all patients who received both a screening and end of study scan of acceptable quality. The primary clinical analysis will be a modified Intent-to-Treat (mITT) approach including all patients randomized and receiving at least one post-baseline assessment.

Per-Protocol (PP) population – All Intent-to-Treat subjects who complete the study (Week 24) and have ingested between 80% and 120% of the protocol prescribed study medication as measured by pill count.

Observed case – An observed case analysis of all patients completing the study will be conducted.

LOCF – Clinical data imputation will use the LOCF approach for missing patients

Responder analysis – Responders will be defined as those that have a significant improvement on brain metabolism on FDG for the whole brain or for any of the pre-specified regions.

A secondary analysis will compare the changes in FDG at 6 months compared to the projected expected metabolism based on the Baseline FDG findings.

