3.2 Secondary Objectives

- To evaluate the efficacy of Rasagiline 1 mg once daily compared to placebo after 24 week treatment on cognition (ADAS-cog), activities of daily living (ADCS-ADL), global function (CIBIC+), and neuropsychiatric symptoms (NPI)
- To evaluate the efficacy of Rasagiline 1 mg once daily compared to placebo after 24 week treatment on measures of executive function (mazes and cancellation of the ADAS-Cog13, Digit Span test, and Controlled Oral Word Association Test [COWAT] for verbal fluency)
- To evaluate the safety and tolerability of Rasagiline as measured by incidence of adverse events/serious adverse events (AEs/SAEs) clinical lab test data, vital signs, 12 lead EKG data, brain MRI finding

4 Populations of Interest

- Intent-to-Treat (ITT) Population: All consented randomized subjects grouped according to the treatment assigned at randomization, regardless of any protocol violations or any crossovers.
- Per-Protocol (PP) Populations: All Intent-to-Treat subjects who meet the inclusion criteria and exclusion criteria specified for enrollment in the protocol, and complete the study (week 24), have ingested between 80% and 120% of the protocol prescribed study medication as measured by pill count, and with no protocol violations that affect the analysis.

5 Analyses Populations: Definitions

- FDG Analyses: The primary FDG analysis will include all patients who received both a screening and end of study scan of acceptable quality.
- Clinical Outcome Analyses: The primary clinical analyses will include the ITT population.
- Safety Analyses: The primary clinical analyses will include the ITT population.
- Responder analysis: Responders will be defined as those that have a significant improvement on brain metabolism on FDG for the whole brain or for any of the pre-specified regions.

6 Enrollment and Participant Flow

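### The 80% pill-count rule takes patients found non-adherent at Week 4 or Week 8 out of the study before the Week 24 FDG scan, so post-randomisation adherence partly decides who enters the primary comparison

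*Protocol*

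**What the plan says.** **The adherence rule.** Protocol 6.4: "Non-adherence of less than 80% of the anticipated dose will result in study discontinuation". The next sentence gives 80% to 120% as accepted compliance, so the rule is read here as adherence below 80%.

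**Withdrawal.** Protocol 5.4 lists "Non-adherence to study regimen as determined by pill count" among the circumstances justifying withdrawal, but its governing sentence is permissive: "The investigator or sponsor may withdraw a patient from the study in the event of an inter-current illness, adverse event, non-compliance, protocol violation". It adds: "Patients who withdraw prior to study completion will be asked to return to the clinic to complete visit 6 (end of study) assessments". Protocol 5.5 says that those who discontinue will be followed, names no scan, and rules out replacement.

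**Scans.** Protocol 9.10 on FDG PET: "The scans will be done at the Screening visit for study eligibility, and at Week 24 visit for end of treatment scan and comparison". Visit 6 (Protocol 7.6 and Table 2) has no FDG PET, tau PET, MMSE or QoL-AD.

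**Analysis sets.** Protocol 11.2 labels as ITT an FDG set limited to patients with both scans of acceptable quality. SAP section 5 uses the same two-scan set for FDG without that label. SAP section 4 defines ITT as all randomised subjects, "regardless of any protocol violations or any crossovers", and section 5 applies it to the clinical and safety analyses. The per-protocol set takes those who complete Week 24 and "have ingested between 80% and 120% of the protocol prescribed study medication as measured by pill count".

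**A different approach elsewhere.** Protocol 9.2, on prohibited or changed concomitant medication, says that "follow-up of all participants, regardless of compliance with medication restrictions, will be continued", with the stated aim of maximising data for the ITT analysis.

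**The concern.** An adherence threshold normally defines a per-protocol set. Here, as 6.4 is worded, it also ends participation. Because the second FDG scan exists only at Week 24 and the primary analysis needs it, a patient removed for low adherence at an earlier visit disappears from the primary comparison.

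Adherence is observed after randomisation and can plausibly follow tolerability or cognitive decline. Removal therefore need not be balanced between arms, and those removed need not resemble those kept. The rule also gives up scans from patients who may be willing to be scanned, in a trial with 25 per arm and no stated dropout allowance. The clinical analyses lose data too: a patient removed at Week 4 contributes no Week 8 or Week 24 scores, and has no post-baseline MMSE or QoL-AD.

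**Working it through.** **1. When the rule can cost a scan.** Adherence is assessed at Weeks 4, 8 and 24, and again at Visit 6 (Table 2). Only the Week 4 and Week 8 counts come before the visit at which the scan is due. At one tablet a day:

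- Weeks 0 to 8: 8 × 7 = 56 doses, counted before the scan visit.
- Weeks 8 to 24: 16 × 7 = 112 doses, first counted at Week 24.
- Share first counted at Week 24: 112/168 = 66.7%.

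A patient fully adherent to Week 8 and 60% adherent afterwards has taken 56 + 0.6 × 112 = 123.2 of 168 doses (73%). That patient reaches the scan visit, is scanned, and fails the per-protocol bound. The contrast between the two-scan set and the per-protocol set is therefore weakened but not emptied.

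**2. How the threshold is read.** 6.4 does not say whether 80% applies per interval or cumulatively. Assuming a per-interval reading and a nominal 28 days to Week 4 (the visit window is ±5 days), six missed tablets give 22/28 = 78.6% and trigger the rule. Had that patient taken every later dose, 24-week adherence would have been 162/168 = 96.4%, inside the per-protocol range. On this reading the rule can remove someone whom the per-protocol adherence bound would have kept.

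**3. The plan's own sample-size figures.** Protocol 11.3 gives, for a 5% SUVr change at two-sided 0.05, 26 per arm at 70% power and 32 at 80%, and for a 10% change 8 per arm at 80%. The SD is not stated, so it is solved from 32 per arm (normal approximation):

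SD = 5 / [(1.960 + 0.842) × √(2/32)] = 7.14% of the mean, so d = 5/7.14 = 0.700.

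- 5% change, 70% power: n = 2 × (1.960 + 0.524)² / 0.700² = 25.2, rounded up to 26.
- 10% change, 80% power: n = 2 × (1.960 + 0.842)² / 1.401² = 8.

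All three figures follow from this one SD.

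**4. Cost of lost scans.** Power = Φ(0.700 × √(n/2) − 1.960), with n scanned pairs per arm. SE inflation = 1/√(1 − loss) − 1. The loss rates are assumptions.

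| Scan loss | Scans lost of 50 | n per arm | SE inflation | Power, 5% change |
|---|---|---|---|---|
| 0% | 0 | 25 | 0% | 69.7% |
| 10% | 5 | 22.5 | 5.4% | 65.1% |
| 20% | 10 | 20 | 11.8% | 60.1% |

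A 20% loss in one arm only (25 against 20) gives 64.6%. For a 10% change, power stays above 98% even at 30% loss (t-test), so precision matters mainly for the smaller effect.

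**5. Bias.** If removal fractions differ between arms by f, and removed patients differ from retained ones by k SD in SUVr change, the bias is roughly k × f SD. Neither quantity can be taken from the documents, so neither sign nor size can be given.

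**The case against.** **The rule may not be mandatory.** 5.4 leaves withdrawal to the investigator or sponsor, and 5.5 promises follow-up. SAP 6.3 defines premature discontinuation as leaving the study and/or stopping treatment, which blurs the two. This stands as an inconsistency: automatic removal is not settled. It does not cure the problem, because nothing in 5.5 brings a withdrawn patient back for a scan.

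**The FDG set is a completer set anyway.** True: the two-scan restriction would exist without 6.4. A reader might infer that 6.4 breaches the SAP's ITT rule for the primary comparison. It does not, because the SAP does not apply ITT to FDG. The tension is with the protocol's ITT label for that set and with the SAP's all-randomised clinical analyses. Protocol 9.2 concerns concomitant medication, so it is a contrast in approach and not a direct contradiction.

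**The Week 24 count need not cost the scan.** A reader might infer from 7.5, which lists the adherence check before the FDG scan, that the rule could cancel the scan that day. The list states no sequence, and no text makes the scan conditional on that count. Nor can it be said that almost every scanned patient would be at or above 80%, since two-thirds of doses are first counted at that visit.

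**No rate is given.** Correct. The loss rates are illustrative. Patients first found below 80% at Week 24 should not be counted as scans lost by rule.

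**Conclusion.** The point holds in limited form. Read together, Protocol 6.4, 5.4, the Visit 6 schedule and the two-scan FDG set make pill-count adherence at Weeks 4 and 8 a condition of entering the primary comparison, for as many patients as the rule is applied to. That fits poorly with the ITT label in Protocol 11.2, with the reason given in 9.2 for continuing follow-up, and with the SAP's all-randomised clinical analyses.

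For a 5% change, planned power of about 70% falls to 65% or 60% at assumed scan losses of 10% or 20%. These figures use an SD back-solved from Protocol 11.3, which describes variation in prefrontal metabolism; if the SD of 24-week change differs, the power levels move. Whether any selection favours drug or placebo cannot be determined from the documents.

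**What to change.** Reconcile Protocol 5.4, 5.5, 6.4, 9.2 and 11.2 with SAP sections 4 and 5:

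- Separate discontinuation of study drug from discontinuation of study assessments, and use the distinction in SAP 6.3 as well.
- State that the scheduled Week 24 FDG PET, tau PET and clinical assessments are sought in all randomised patients who have not withdrawn consent, regardless of pill-count adherence.
- Use the 80% to 120% bound to define the per-protocol set, and say whether it is judged per interval or over 24 weeks.
- Align the ITT label for the FDG set with the SAP.

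Whether and when study drug is stopped for non-adherence remains the sponsor's decision; no rule is proposed here.

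The cost is a short amendment. The visits and scans are already scheduled for every randomised patient, although the documents give no budget. The downside is a slightly diluted mean exposure in the primary set, which the per-protocol analysis is there to address. SAP section 9 promises that repeat only within its section on clinical measures, so one line should extend it to FDG.
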